5.1. Primary Efficacy Endpoints

- Proportion of subjects with an improvement of ≥ 4 from baseline in PP NRS at Week 16
- Proportion of subjects with an IGA success (defined as an IGA of 0 [Clear] or 1 [Almost clear] and a ≥ 2 -point improvement from baseline) at Week 16

5.2. Key Secondary Efficacy Endpoints

The key secondary efficacy endpoints are as follows:

- Proportion of subjects with an improvement of ≥ 4 from baseline in PP NRS at Week 4
- Proportion of subjects with PP NRS < 2 at Week 16
- Proportion of subjects with an improvement of ≥ 4 from baseline in SD NRS at Week 16
- Proportion of subjects with an improvement of ≥ 4 from baseline in SD NRS at Week 4
- Proportion of subjects with PP NRS < 2 at Week 4

5.3. Secondary Efficacy Endpoints

The secondary efficacy endpoints are as follows:

- IGA success rate at each visit through Week 24
- Proportion of subjects with IGA ≤ 2 at each visit through Week 24
- Percentage of pruriginous lesions with excoriations/crusts (Prurigo Activity Score [PAS] item 5a) at each visit through Week 24
- Percentage of healed prurigo lesions (PAS item 5b) at each visit through Week 24
- Change from baseline in number of lesions in representative area (PAS item 4) at each visit through Week 24
- Proportion of subjects with number of pruriginous lesions (PAS item 2) < 20 at each visit through Week 24
- Proportion of subjects with an improvement of ≥ 4 from baseline in PP NRS through Week 24
- Proportion of subjects with PP NRS < 2 from baseline through Week 24
- Proportion of subjects with PP NRS < 3 from baseline through Week 24
- Absolute change from baseline in PP NRS through Week 24
- Percent change from baseline in PP NRS through Week 24
- Proportion of subjects with an improvement of ≥ 4 from baseline in Average Pruritus (AP) NRS through Week 24
- Proportion of subjects with PP NRS improvement ≥ 4 from baseline and IGA success at Week 16, Week 20 and Week 24

This document is confidential.

- Proportion of subjects with AP NRS < 2 from baseline through Week 24
- Absolute change from baseline in AP NRS through Week 24
- Percent change from baseline in AP NRS through Week 24
- Proportion of subjects with an improvement of ≥ 4 from baseline in SD NRS through Week 24
- Absolute change from baseline in SD NRS through Week 24
- Percent change from baseline in SD NRS through Week 24
- Change from baseline in sleep diary endpoints (sleep onset latency, wakefulness after sleep onset [WASO], total awake time, total sleep time, sleep efficiency, WASO related to PN, number of WASO related to PN) based on recordings from subject sleep diary through Week 24
- Distribution of PN-associated pain frequency through Week 24
- Proportion of subjects with PN-associated pain frequency rating = 5 (every day) at each visit through Week 24
- Change from baseline in PN-associated pain intensity through Week 24
- Percentage change from baseline in PN -associated pain intensity at each visit through Week 24
- Proportion of subjects reporting low disease activity (clear, almost clear, or mild) based on Patient Global Assessment of Disease (PGAD) at Week 24
- Proportion of subjects satisfied with study treatment (good, very good, or excellent) based on Patient Global Assessment of Treatment (PGAT) at Week 24
- Proportion of subjects with an improvement of ≥ 4 in Dermatology Life Quality Index (DLQI) through Week 24
- Change from baseline in DLQI through Week 24
- Change from baseline in Hospital Anxiety and Depression Scale (HADS) for each subscale (i.e., depression and anxiety) at Week 24
- Change from baseline in EuroQoL 5-Dimension (EQ-5D) at Week 24

5.4. Pharmacokinetic Endpoints

- Nemolizumab (CD14152) serum concentrations

5.5. Immunogenicity Endpoints

- ADA assay (screening, confirmatory, final, titer, NAb)

5.6. Safety Endpoints

- Incidence and severity of AEs, including TEAEs, AESIs, SAEs and Adjudicated AEs
- Clinical laboratory tests
- Vital signs
- Electrocardiogram
- Physical examination

This document is confidential.

- Respiratory assessment including respiratory examination, Peak expiratory flow, and Asthma Control Test (ACT)

This document is confidential.

6. Analysis Sets

6.1. Screened Population

The Screened population comprises all subjects who signed the ICF and have screening data entered into the database. This population includes screen failures and randomized subjects. Screen failed subjects are defined as those subjects who fail to meet inclusion criteria or meet exclusion criteria and discontinue the study prior to randomization. Subjects that are re-screened will only be counted once, under the subject ID assigned for the repeat screening.

Unless specified otherwise, this set will be used for subject listings and summaries of subject disposition.

6.2. Intent-to-Treat Population

The Intent-to-Treat (ITT) population will consist of all randomized subjects. The ITT population will be the primary population for efficacy analyses. All analyses under the ITT population will be analyzed under the treatment group as randomized.

6.3. Per-Protocol Population

The Per-Protocol (PP) population will consist of all subjects in the ITT population and have no major protocol deviations that would have a significant effect on the efficacy of the study treatment (see [Section 6.6](#)). Primary, key secondary and selected secondary endpoints will be analyzed using the PP population, under the treatment group as randomized.

6.4. Safety Population

The Safety (SAF) population will consist of all randomized subjects who received at least 1 administration of study drug. The treatment group assignment in this population will be defined by the treatment actually received. This population will be used for the analyses of safety.

6.5. Pharmacokinetic Analysis Population

The PK analysis population will consist of all subjects included in the SAF, with at least one measurable post-baseline PK assessment. Similar to SAF, the treatment group assignment in this population will be defined by the treatment actually received. This population will be used for the descriptive analyses of PK concentrations.

6.6. Protocol Deviations

Protocol deviations will be recorded by the Clinical Research Associate (CRA) in the Clinical Trial Management System (CTMS). All protocol deviations will be categorized by the associated deviation type and will be assessed individually on a regular basis on whether they are major or minor. Details can be found in the Protocol Deviation and Non-compliance Management Plan.

Major protocol deviations that are analysis relevant lead to an exclusion of the subject from the per-protocol population. A case by case decision regarding exclusions of subjects from the per-protocol analysis will be made in a blind data review meeting (BDRM) which will take place prior to unblinding the study. The criteria for exclusion from the PP population will be specified in the BDRM Preparation Plan. Only major protocol deviation which have a significant effect on the primary efficacy will result in exclusion from the PP population.

A summary table for number and percentage of subjects with major protocol deviation will be generated by type of deviation and treatment group for the ITT population.

This document is confidential.

Protocol deviations incurred as a direct result of the COVID-19 pandemic should be specifically recorded and presented as a COVID-19 deviation. The number and percentage of subjects with major (including major COVID-19) deviation will be provided by type of deviation and treatment group for the ITT population and additionally provided by Site.

All protocol deviations and the protocol deviations related to COVID-19 will be listed for the ITT population.

This document is confidential.

7. Estimands

The primary and key secondary efficacy endpoints will be evaluated and assigned to treatment at the time of randomization based on ITT population. The estimand is defined to address the scientific question relevant to subjects who are able to complete treatment with a response assessment without further medication being required, other than the allowed rescue medication.

An intercurrent event is an event which occurs after start of treatment and thus complicates the description and interpretation of treatment effects. [Table 7-1](#) below lists potential intercurrent events and the strategy to deal with them for the estimand. The estimands for endpoints are defined in [Table 7-2: Estimands for Co-primary Endpoints \(2 endpoints\)](#) and [Table 7-3](#).

Table 7-1: List of Intercurrent Events

Intercurrent Event	Strategy to Deal With Intercurrent Event (ICE) Within Analysis	Assessment of Subject
Treatment discontinuation	Treatment-policy strategy	Use observed response.
Rescue therapy	Composite strategy (Continuous endpoints & Binary endpoints)	Subjects will be treated as treatment failures on or after rescue therapy. The values of the variable of interest collected on or after the use of rescue therapy will be set to the worst possible value of the score. For diary data, if subject took rescue therapy within the analysis visit window, weekly average on or after visit window will be computed as 'worst-case value'. Subject's binary response will be calculated based on the underlying value.
Rescue therapy	Hypothetical strategy (Continuous endpoints)	Subject will be treated as treatment failures on or after intake of rescue therapy and will be considered as missing before running MMRM analysis. For diary data, if subject took rescue therapy within analysis visit window, weekly average on or after visit window will also be considered missing before running MMRM analysis. Treatment effect estimated by MMRM model assumes the subject with ICEs would have followed same as other subjects in the same treatment. Applicable only for the MMRM analysis.

This document is confidential.

Table 7-2: Estimands for Co-primary Endpoints (2 endpoints)

Endpoints	Estimands
Proportion of subjects with an improvement of ≥ 4 from baseline in PP NRS at Week 16	
Population: ITT population
 
Endpoint: a binary response indicates if subjects have a change from Baseline of ≥ 4 at Week 16
 
Intercurrent events: use of rescue therapies on or prior to Week 16 is considered as treatment failure; the observed response at Week 16 after treatment discontinuation will be used in the analysis
 
Summary measure: treatment difference of Nemolizumab and placebo in response rate

Proportion of subjects with an IGA success (defined as an IGA of 0 [Clear] or 1 [Almost clear] and a ≥ 2 -point improvement from baseline) at Week 16	
Population: ITT population
 
Endpoint: a binary response indicates if subjects have IGA of 0 [clear] or 1 [almost clear] and a ≥ 2-point reduction from Baseline at Week 16
 
Intercurrent events: use of rescue therapies on or prior to Week 16 is considered as treatment failure; the observed response at Week 16 after treatment discontinuation will be used in the analysis
 
Summary measure: treatment difference of Nemolizumab and placebo in response rate

Table 7-3: Estimands for Key Secondary Endpoints (5 endpoints)

Endpoints	Estimands
Proportion of subjects with an improvement of ≥ 4 from baseline in PP NRS at Week 4	
Population: ITT population
 
Endpoint: a binary response indicates if subjects with an improvement of PP NRS ≥ 4 at Week 4
 
Intercurrent events: use of rescue therapies on or prior to Week 4 is considered as treatment failure; the observed response at Week 4 after treatment discontinuation will be used in the analysis
 
Summary measure: treatment difference of Nemolizumab and placebo in response rate

Proportion of subjects with PP NRS < 2 at Week 16	
Population: ITT population
 
Endpoint: a binary response indicates if subjects with PP NRS < 2 at Week 16
 
Intercurrent events: use of rescue therapies on or prior to Week 16 is considered as treatment failure; the observed response at Week 16 after treatment discontinuation will be used in the analysis
 
Summary measure: treatment difference of Nemolizumab and placebo in response rate

This document is confidential.

Endpoints	Estimands
Proportion of subjects with an improvement of ≥ 4 from baseline in SD NRS at Week 16	
Population: ITT population
 
Endpoint: a binary response indicates if subjects with an improvement of SD NRS ≥ 4 at Week 16
 
Intercurrent events: use of rescue therapies on or prior to Week 16 is considered as treatment failure; the observed response at Week 16 after treatment discontinuation will be used in the analysis
 
Summary measure: treatment difference of Nemolizumab and placebo in response rate

Proportion of subjects with an improvement of ≥ 4 from baseline in SD NRS at Week 4	
Population: ITT population
 
Endpoint: a binary response indicates if subjects with an improvement of SD NRS ≥ 4 at Week 4
 
Intercurrent events: use of rescue therapies on or prior to Week 4 is considered as treatment failure; the observed response at Week 4 after treatment discontinuation will be used in the analysis
 
Summary measure: treatment difference of Nemolizumab and placebo in response rate

Proportion of subjects with PP NRS < 2 at Week 4	
Population: ITT population
 
Endpoint: a binary response indicates if subjects with PP NRS < 2 at Week 4
 
Intercurrent events: use of rescue therapies on or prior to Week 4 is considered as treatment failure; the observed response at Week 4 after treatment discontinuation will be used in the analysis
 
Summary measure: treatment difference of Nemolizumab and placebo in response rate

This document is confidential.

8. General Aspects for Statistical Analysis

8.1. General Methods

- All data will be listed, and summary tables will be provided.
- Unless otherwise specified, summaries will be presented for each treatment and overall, if indicated, by visit.
- Continuous variables will be summarized using the number of observations (n), mean, standard deviation (SD), median, 1st Quartile (Q1), 3rd Quartile (Q3), minimum, and maximum. Categorical variables will be summarized using number of observations (n), frequency and percentages of subjects in each category.
- Unless otherwise stated, all statistical tests will be two-sided and conducted at the 5% level; all presented confidence intervals (CIs) will be two-sided 95% CIs.

8.2. Key Definitions

Screening period is a period of up to 4 weeks before Baseline/Day 1 during which subject eligibility is evaluated. Subjects receiving rescue therapies during the screening period are not eligible to participate in the study.

The 24-week **treatment period** is defined as Baseline/Day 1 to Week 24. If early discontinued during treatment period, it is defined as the period until 4 weeks (<=28 days) after last dosing date or early termination date whichever is earlier.

Follow-up period is defined as the post end of treatment period to follow-up visit in respective treatment period.

The **Baseline value** is defined as the last non-missing value before the first dose of study drug. In case that the date of first injection is not available, the date of randomization is considered.

For diary data (PP NRS, SD NRS), the Baseline values will be derived from data collected during the 7 days prior to the first administration of study drug, if subject is treated. Otherwise, the data collected during 7 days prior to randomization will be used. Baseline score will be the weekly prorated average of non-missing subject diary scores reported during the 7 days. A minimum of 4 daily scores out of the 7 days is required to calculate the weekly prorated average score. If there are less than 4 non-missing assessments in the baseline diary window, the interval lower bound can be extended up to 7 additional days, one day at a time, to obtain the most recent 4 non-missing values. For sensitivity analysis, a minimum of 2 or 3 daily scores out of the 7 days will be used to calculate the weekly prorated average score for primary and key secondary endpoints and the interval will not be extended with additional days.

The **date of first treatment** is defined as the date of first injection of study drug.

The **date of last treatment** is defined as the date of last injection of study drug.

Study day is defined as the number of days from the date of first treatment (randomization date if not treated) and will be calculated as follows:

- If the event date \geq date of first treatment, then study day = event date - date of first treatment + 1. Treatment Day 1 is therefore defined as the day of first treatment.

This document is confidential.

- If the event date < date of first treatment, then study day = event date - date of first treatment.
- If subject is randomized, but not treated and event date \geq date of first treatment, then study day = event date - date of randomization.
- If subject is randomized, but not treated and event date < date of first treatment, then study day = event date - date of randomization.

A subject's **date of last participation** in the trial is the last date of contact and is recorded as the date of completion or date of withdrawal on the completion page of the case report form (CRF).

Only the **subjects infected by COVID-19** during study participation will be considered subjects with COVID-19 infection.

8.3. Missing Data

The primary method to impute the missing values will be as follows:

Continuous Endpoints: For continuous secondary endpoints (except EQ-5D, HADS) during treatment period, the MI under MAR assumption approach and the MMRM approach will be used to handle the missing data.

Binary Endpoints: All missing values will be treated as a non-responder for the binary endpoints for primary, key secondary and secondary endpoints. To assess the robustness of non-responder analysis for primary and key secondary endpoints, a tipping point analysis will be performed. The MI under MAR assumption, last observation carried forward (LOCF) approach, and observed case (OC) approach will be used as sensitivity analysis to impute the missing values for the primary and key secondary endpoints. If applicable, the continuous response will be imputed first, and the response will then be categorized.

Use of rescue therapy: All efficacy data, except OC, will be treated as treatment failure. Binary endpoints will be based on the underlying values and continuous variables will be imputed using the worst case score (questionnaires) or worst case value (diary data), on or after rescue therapy is used, independent if visit was attended or not. This procedure will be completed before imputing missing data under different assumptions (i.e., non-responder, LOCF, MI under MAR/MNAR). A different approach will be applied for MMRM analysis where data on or after rescue therapy will be considered as missing before applying MMRM analysis.

In OC analysis, no observed data after subject has received rescue treatment will be excluded. There will be no imputations for missing data.

Adverse events and concomitant medications/procedures: Missing assessment times will have imputed times for the purposes of assessing treatment emergence for AEs or classifying medications/procedures into prior/concomitant. However, the assessment date and time (start date, stop date, and time if collected from CRF) without imputation will be presented in the listings.

For the start of a concomitant medication/procedure or AE:

- Only the year is reported: If the subject received the first study drug dose in the year reported, then the date of the first dose of study drug will be used as the start date; otherwise, January 1 of the year reported will be used as the start date.

This document is confidential.

- The month and year are reported: If the subject received the first study drug in the month and year reported, then the date of the first dose of study drug will be used as the start date; otherwise, the first day of the month and year will be used as the start date.
- The time is collected but missing: If the start date is the same as the date the subject started receiving study drug, then the time of the first dose of study drug will be used as the start time; otherwise, 00:00 will be used as the start time.

For the end of a concomitant medication/procedure or AE:

- Only the year is reported: The earlier between December 31 of the year reported and the date of the last study contact with the subject will be used as the stop date.
- The month and year are reported: The earlier between the last date of the month and year reported and the date of the final contact with the subject will be used as the stop date.
- The time is collected but missing: 23:59 (or 23:59:59 if collected up to seconds) will be used as the stop time.

If an AE has the start date completely missing and the stop date on/after the first dose date of study drug, this AE will be considered as treatment emergent (TEAE).

If a medication/procedure has the stop date completely missing, this medication/procedure will be considered as ongoing and concomitant. If the start date of a medication/procedure is completely missing and impossible to identify different by stop date, this medication will be considered as concomitant.

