10.3.10. Hospital Anxiety and Depression Scale (HADS)

HADS is a 14-question validated questionnaire completed by the subject. Each question has a multiple choice answer which is scored between 0 and 3. Questions are identified as relating to anxiety (A) or depression (D) and a summation for each area is performed leading to a total score of 0 to 21 for each area. Scores of 0 to 7 are considered normal, 8 to 10 are borderline, and ≥ 11 indicate clinical effects.

HADS will be collected at Baseline/Day 1, Week 16, Week 24 and Early Termination and subscales will be summarized separately for each subscale (Total Score Anxiety and Total Score Depression) as continuous variable using OC for Baseline, Week 16 and Week 24 on the ITT population. Absolute change from Baseline in HADS subscale scores will also be summarized.

Absolute change from Baseline in HADS subscale scores will be analyzed for Week 16 and Week 24 using ANCOVA using observed case, including treatment group, analysis center and body weight at randomization cut-off (< 90 kg and ≥ 90 kg) as factor and baseline as covariate. The LSMeans, standard error of LSMeans, and 95% CI for change from baseline, as well as the difference in LSMeans between the treatment groups, the two-sided 95% CI, and associated p-value will be presented.

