10.3.11. EuroQoL 5 Dimension Instrument

The EQ-5D instrument is a validated questionnaire, completed by the subject and consists of 2 parts. The first part consists of 5 multiple choice QoL questions and the second is a 100 point VAS scale with 0 being “Worst imaginable health state” and 100 being “Best imaginable health state”.

This document is confidential.

EQ-5D VAS will be collected at Baseline/Day 1, Week 16, Week 24 and Early Termination and be summarized as a continuous variable using OC for Baseline, Week 16 and Week 24 on the ITT population. Absolute change from Baseline in EQ-5D VAS will also be summarized using OC.

Absolute change from Baseline in EQ-5D VAS at Week 16 and Week 24 will be analyzed using ANCOVA using observed case, including treatment group, analysis center and body weight at randomization cut-off (< 90 kg and ≥ 90 kg) as factor and baseline as covariate. The LSMeans, standard error of LSMeans, and 95% CI for change from baseline, as well as the difference in LSMeans between the treatment groups, the two-sided 95% CI, and associated p-value will be presented.

Five dimensions of EQ-5D (mobility, self-care, usual activities, pain/discomfort, and anxiety/depression) will be summarized as a categorical variable using OC.

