13.6.3. Asthma Control Test

Subjects with a medical history of asthma will take an Asthma Control Test (ACT) at Screening, Baseline/Day 1, Week 4, Week 8, Week 12, Week 16, Week 20, Week 24, Early Termination visit, and Week 32/Follow-up. Subjects with de novo asthma will complete the ACT testing beginning from de novo diagnosis and at all subsequent scheduled visits.

The ACT is composed of 5 questions. For each question, the subject will choose the best answer out of 5 possible answers. The test provides a numerical score ranging from 5 to 25 to assess asthma control; a higher score indicates better asthma control while a score of 19 or less indicates the subject's asthma may not be under control.

ACT total score (absolute values and change from Baseline) will be summarized as a continuous variable (Baseline and scheduled visits only).

The number and percentage of subjects with an ACT score ≤ 19 will be summarized (scheduled visits only).

The ACT results and the ACT score will be listed on the Safety population.

This document is confidential.

14. Changes from Analysis Planned in Protocol

In protocol Section 9.10 (Prior and Concomitant Therapy), concomitant medications/therapies are defined as any therapies taken during the study (i.e., from the screening visit to the end of study).

However, for the analysis purpose, concomitant medications/therapies are defined as medications/therapies which start or stop or ongoing on or after the 1st injection of study drug.

In protocol stratification variable weight is named 'body weight at baseline'. This wording is corrected to 'weight at randomization', to clarify that this is the body weight at the time of randomization and how this information is provided by the investigator.

It has been further clarified how to deal with data collected on or after the use of rescue therapy in order to consistently treat subjects as treatment failures across all the analyses. Efficacy data collected on or after the use of rescue therapy will be set to the worst case value for continuous variables and subject's binary response will be calculated based on the underlying continuous values as stated in [Section 8.3](#).

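### HADS and EQ-5D VAS are tested only on observed cases, so the Week 24 comparison drops subjects whose Week 16 score is known; the SAP's own MMRM would use it

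*SAP*

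**What the plan says.** Section 8.3 sets the general rule and its exception: "For continuous secondary endpoints (except EQ-5D, HADS) during treatment period, the MI under MAR assumption approach and the MMRM approach will be used". Section 10.3 repeats the exception for EQ-5D and HADS. The endpoint sections carry it out:

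- HADS (10.3.10): "Absolute change from Baseline in HADS subscale scores will be analyzed for Week 16 and Week 24 using ANCOVA using observed case".
- EQ-5D (10.3.11): "Absolute change from Baseline in EQ-5D VAS at Week 16 and Week 24 will be analyzed using ANCOVA using observed case".
- In both sections the LSMeans difference comes with inference: "the two-sided 95% CI, and associated p-value will be presented".

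Table 10-1 lists ANCOVA as the only test for these scores. The index of tables has one inferential table for HADS (14.2.3.11.2) and one for EQ-5D VAS (14.2.3.12.3), both ANCOVA on observed cases. Section 5.3 defines both endpoints at Week 24. The SAP gives no reason for the exemption.

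Section 8.3 also defines observed case (OC): "In OC analysis, no observed data after subject has received rescue treatment will be excluded. There will be no imputations for missing data". For other analyses of continuous endpoints, Table 7-1 has values "collected on or after the use of rescue therapy will be set to the worst possible value of the score", or treats them as missing when an MMRM is fitted.

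**The concern.** A separate ANCOVA at Week 24 on subjects with a Week 24 score adjusts for arm, analysis center, weight group and baseline, and for nothing observed after baseline. It is unbiased only if, given those variables, missingness at Week 24 is unrelated to outcome. A poor Week 16 score is an obvious reason to leave, and the analysis ignores it. If this happens more in one arm, the remaining subjects in that arm look too good.

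Three p-values are at stake, and there is no MI, MMRM or sensitivity analysis to set beside them. DLQI, another questionnaire with the same Week 16 and Week 24 windows, gets both MI-ANCOVA and MMRM.

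**Working it through.** The SAP states no figure for this point, so there is none to reproduce. The check has three parts.

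**1. Who is lost.** Table 8-1 windows all visits, including early termination. For HADS and EQ-5D:

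| Day of last score | Assigned to | Effect on the Week 24 ANCOVA |
|---|---|---|
| 2-60 | Week 1 (not an analysis visit for these scores in Table 10-1) | excluded; no post-baseline score that an MMRM could use |
| 61-154 | Week 16 | excluded, although the Week 16 score is known |
| 155-210 | Week 24 | included |

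The avoidable loss is the middle row. The Week 16 ANCOVA does include those subjects, so the problem concerns Week 24 only.

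**2. Upper limit on numbers.** Section 4.3 gives 270 subjects (180 v 90) and 15% dropout over the treatment period.

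- Remaining: 180 x 0.85 = 153 and 90 x 0.85 = 76.5, together 229.5. About 40 of 270 could be missing at Week 24.
- Standard error factor of a mean difference, sqrt(1/n1 + 1/n2): 0.129 SD with 180 v 90 and 0.140 SD with 153 v 76.5, a rise of 8.5%.

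The MMRM can recover only the part of this loss that falls in the middle row.

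**3. Bias.** Nothing below except the 15% dropout figure comes from the SAP.

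HADS-like scale. Assumed: true Week 24 difference -1.7, SD 4, correlation 0.75 between visits, logistic dropout between Weeks 16 and 24 driven by the Week 16 change. Bias = 1 - estimate / (-1.7). Pooled dropout = (180 x rate + 90 x rate) / 270.

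| Late dropout, nemolizumab v placebo | Pooled dropout | Week 24 OC estimates | Bias |
|---|---|---|---|
| 15% v 15% | 15% | no material bias | about 0 |
| 5% v 10% | (9 + 9)/270 = 6.7% | -1.64 to -1.68 | about 1-4%; 1-5% across all runs |
| 12.5% v 20% | (22.5 + 18)/270 = 15% | -1.61 to -1.65 | about 3-5% |
| 10% v 25% | (18 + 22.5)/270 = 15% | -1.53 to -1.58 | about 7-10%; up to 13% across all runs |
| 15% v 30% | (27 + 27)/270 = 20% | -1.50 to -1.66 | about 2-12% |

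A missing-at-random (MAR) analysis that uses the Week 16 score gave -1.70 to -1.71 at 12.5% v 20% and 10% v 25%.

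SD-unit version. Assumed: true difference 0.40 SD, dropout driven by the Week 16 score with a logistic slope of 1 per SD, Week 16-24 correlation 0.5, 0.7 and 0.85.

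- 15% v 15%, same dependence in both arms: 0.401, 0.399, 0.405. No bias.
- 10% v 25%, same dependence: 0.367, 0.348, 0.329, that is 8%, 13% and 18% too small.
- Dependence in the placebo arm only: 0.318 to 0.362 at 15% v 15%, and 0.266 to 0.347 at 10% v 25%.
- The analysis using Week 16 stayed between 0.396 and 0.404 throughout.

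So equal dropout protects the OC estimate only if the reasons for leaving are also the same in both arms.

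**The case against.** **A contradiction with Section 14?** A reader might infer one, because that section says the rescue rule was clarified "in order to consistently treat subjects as treatment failures across all the analyses". The documents do not support it. The same paragraph defers to Section 8.3, which excludes OC from the rule, and the closing note of Section 10.3 does so again. The exemption is explicit and consistent.

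**Do post-rescue scores count as response?** No. HADS and EQ-5D VAS are continuous and have no responder definition. Post-rescue scores are analysed as observed, which is a defensible choice for generic measures of mood and health status.

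**Is DLQI a fair comparison?** Only in part. DLQI is also collected at Week 4. HADS and EQ-5D have no post-baseline analysis visit before Week 16, so an MMRM gains nothing for subjects who leave before day 61. DLQI is also summarised on observed cases, so the results can still be compared on that basis.

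**Is the bias large?** Several features limit it. Subjects who stop drug or need rescue are asked to attend through Week 24 (Section 4.1), and early termination scores from day 155 count as Week 24. The SAP's 15% covers the whole treatment period, so placing all of it after Week 16 is severe, and 15% v 30% exceeds it. With more dropout on placebo the bias runs against the drug.

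**Should the whole DLQI approach be copied?** No. Its MI-ANCOVA would set post-rescue HADS subscales to 21 and VAS to 0. Assume 20% v 5% rescue use and an observed HADS score of 6 to 10. The worst-case rule then moves the difference by 0.15 x (21 - 10) = 1.65 to 0.15 x (21 - 6) = 2.25 points. Keeping observed scores with an assumed 2-point rescue benefit moves it by 0.15 x 2 = 0.3. That remedy could do more than the problem it repairs.

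These objections limit the size and the remedy. None explains why a known Week 16 score should be left out of the Week 24 analysis.

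**Conclusion.** The concern holds as a weak choice of method. The only test of HADS-A, HADS-D and EQ-5D VAS at their Week 24 endpoint time discards subjects with a known Week 16 score.

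On the HADS-like inputs, 1-5% of an assumed 1.7-point difference is at most 1.7 x 0.05 = 0.09 points, and 3-13% is at most 1.7 x 0.13 = 0.22 points. Stronger dependence of dropout on the Week 16 score, or dependence in one arm only, gives more. The SAP supplies no data to choose among these settings. The direction would reverse if poor responders left more often on nemolizumab.

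The endpoints lie outside the fixed sequence of Section 10, so no confirmatory claim depends on them. The change is worth making because the better model is already specified, but it is not critical.

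**What to change.** - In Sections 8.3 and 10.3, remove the exemption of HADS and EQ-5D from the MMRM.
- In 10.3.10 and 10.3.11, analyse HADS-A, HADS-D and EQ-5D VAS at Weeks 16 and 24 with the MMRM described in Section 10.3: visit, treatment, analysis center, weight group, baseline, baseline-by-visit and treatment-by-visit. Follow the text of 10.3, because the example MMRM code in Section 21.3 omits the baseline-by-visit term.
- Set post-rescue values to missing, as in the SAP's other MMRM analyses. Do not require worst-case imputation after rescue for these scores.
- Keep the observed-case ANCOVA as supportive, so that results using post-rescue scores as observed remain visible.
- Update Table 10-1 and the index of tables.

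The cost is SAP wording, reuse of existing MMRM programs and a few extra tables. The MMRM also has a limit that the SAP should state: it relies on MAR for post-rescue values as well as for missed visits.
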